There will be no additional costs to patients due to study procedures. Patients will be billed for their care per treatment received during their hospitalization per usual. Oxytocin is very inexpensive. Any increase in charge due to the high dose oxytocin protocol will be billed to the Department of OB/GYN. The department has awarded a small internal funding to cover the administrative and additional medication cost of this study.

10) Risks to subjects

Low dose oxytocin regimen is the current standard of care on labor and delivery in the United States. High dose oxytocin regimen is widely used internationally. Both regimens' safety profile has been compared and validated in multiple meta-analysis including a Cochrane review as detailed above in the background section. Therefore, the American College of Obstetricians and Gynecologists had endorsed both regimens. It is important to emphasize that the following risks pertain to both the low dose (the current standard of care on L&D) and high dose protocol, and that the Cochrane review did

not find the high dose protocol to have additional risks to patients. Adverse events (AE) and serious adverse events (SAE) to oxytocin in mother includes:

Cardiovascular: Cardiac arrhythmia, including premature ventricular contractions (SAE), subarachnoid hemorrhage (SAE), tachycardia (SAE), hypotension (SAE), hypotension (SAE)

As discussed above, cardiovascular changes with high dose oxytocin were observed in studies in which patients received a large intravenous bolus over a short period (15-30 seconds). Secondary to these concerns, currently the standard of care is to administer oxytocin over a slow intravenous infusion ^{1,2}. This study does not deviate from the standard of care protocol. Therefore, the investigator predicts a low cardiovascular risk to patients, risks that would be comparable with current standard of care. In addition, the investigator excluded mothers with previous serious cardiac disease to further decrease risks to subjects.

Genitourinary: Uterine hypertonia (SAE), tachysystole (AE), uterine rupture (SAE), postpartum hemorrhage (SAE)

These are well known side effects of oxytocin on the obstetrical floor and the absolute rates remain low. Again, as discussed above, these risks were evaluated and compared directly by multiple meta-analysis and a Cochrane review. There was also no difference in serious maternal or neonatal morbidity or death between the high and low dose regimen. There was no difference in adverse outcomes, including maternal uterine rupture, postpartum hemorrhage, endometritis, estimated blood loss, abnormal fetal heart tracing, fetal Apgar, newborn resuscitation and neonatal intensive care unit admission ³⁻⁵. Therefore, the investigator believes that the risk to the patient will be similar to baseline.

Tachysystole will be monitored continuously as a clinical parameter to direct patient care and protocol management as well as a secondary outcome variable.

Endocrine and metabolic: Water intoxication (SAE), hyponatremia (SAE)

Again, as described above, there were also old case reports originating from the 1970s about concerns over high dose oxytocin and its association with maternal hyponatremia or water intoxication ^{6,7}. The hypothesis behind its association is due to the similarity between oxytocin and anti-diuretic hormone. These were largely single case reports in the setting of accidental large overdose of oxytocin in addition to large volume administration of electrolyte-free solutions. Since then, the practice of administering oxytocin is only given alongside isotonic lactated ringer or normal saline in a slow intravenous infusion fashion ^{8,9}. This study does not deviate from the standard of care. Therefore, the investigator predicts a low risk to patients, risks that would be comparable with current standard of care.

The following SAE and AE have been associated with oxytocin but frequency is not well defined and not well reported in the literature.

Hematologic: pelvic hematoma (SAE), fatal afibrinogenemia (SAE)

Misc: Anaphylactic reaction (SAE), nausea and vomiting (AE)

Risks to fetus include:

Due to induced uterine motility: bradycardia (SAE), premature ventricular contractions and other arrhythmias (SAE), permanent CNS or brain damage (SAE), fetal death (SAE), neonatal seizures (SAE)

Due to use of oxytocin in mother: low apgar scores (AE), neonatal jaundice (AE), neonatal retinal hemorrhage (SAE)

Frequency of risks:

The frequency of risks occurring for each risk is not well defined and not well reported in the literature. All above risks are considered to be rare, with the exception of:

Tachysystole: This will be monitored continuously as a clinical parameter to direct patient care and protocol management, as written in the protocol. Also it is important to recognize that tachysystole occurs with the low dose protocol as well, which is the current standard of care.

Nausea and vomiting: This is a common side effect of labor itself with or without oxytocin.

It is important to recognize that these risks exist equally in the low dose protocol, which is the current standard of care on Labor and Delivery. When a patient presents for an induction of labor with oxytocin, they are subjected to all of the above risks, regardless of whether they are enrolled as a study participant. The only way to avoid these risks completely, is for a patient to not receive oxytocin (which is required if patient agreed to undergo an induction of labor). These risks above have been well monitored throughout clinical practice since the 1970s, and large Cochrane review as detailed above had provided good safety profile for this drug in both the low and high dose regimen.

All serious adverse events (SAE) will be monitored and documented closely during the study, and will result in discontinuation of the study protocol immediately. The management of AE is detailed in the protocol. If more than 20% of patients enrolled in the study have an AE/SAE, enrollment in the study will be stopped pending an evaluation of the frequency of AE/SAE.

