It is possible that previously eligible and consented patients will become ineligible when they present to labor and delivery, because they could have gone into labor on their own or rupture their membrane prior to presentation to labor and delivery. In this case, the patient will be considered a screen failure.

b. Informed Consent: The consent process was described above. All consent will be documented in written format. It will be communicated to the patients that there will be no change in their clinical care, regardless if patient agreed to consent with this study. For example, participation in this study does not affect the options for pain management during labor routinely available to the patient. This will minimize the potential for coercion. Patients who decline enrollment in the trial will have the method of induction chosen by their physician. Additionally, as this study is an induction of labor study, patients will be recruited and consented prior to going into labor so that the consent process is not completed under stress.

8) Research procedures involved in the Human Research

Sequence generation for randomization, Allocation method and Blinding

This portion of the study will be carried out by the research pharmacy. Single (low dose) and triple (high dose) concentration of oxytocin will be premixed in the intravenous fluid bag in the pharmacy. Sequence generation for randomization will be created with 1:1 ratio in both the obese and lean group by the Department of Statistics. After the sequence is generated, this list will be given to the research pharmacy. The premixed oxytocin medication will be sequentially labelled as "OPS drug, patient #1, 2, 3" etc. per the allocation. Allocation concealment will also be carried out by pharmacy as these bags will completely appear identical after they are labelled numerically. Once a patient is randomized, the pharmacy will send up the appropriate concentration of oxytocin already premixed in the intravenous fluid bag, labelled as "OPS drug, patient #". Lean group will be assigned at #1-70 and obese group will be assigned at #71-140.

Through the above process, the concentration of the drug will be blinded to the investigators, providers, patient and analysts. The patient will continue to have the same concentration of oxytocin until delivery.

Study Drug (please see appendix B)

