Low dose oxytocin regimen (the standard at Banner University Labor and Delivery, as well as across the United States): 30 units in 500cc 0.9% normal saline bag (60 miliunit/cc). Starting rate would be 2 miliunit/minute, or 2cc/hour. The medication will be increased by 2 miliunit/minute = 2cc/hr every 30 minutes until adequacy of contraction or cervical change. At 20 miliunit/minute = 20cc/hr, provider will assess patient for eligibility to continue to increase oxytocin dosage.

High dose oxytocin regimen (endorsed by American College of Obstetricians and Gynecologists): 90 units in 500cc 0.9% normal saline bag (180 miliunit/cc). Starting rate would be 6 miliunit/minute, or 2cc/hour. The medication will be increased by 6 miliunit/minute = 2cc/hr every 30 minutes until adequacy of contraction or cervical change. At 60 miliunit/minute = 20cc/hr, provider will assess patient for eligibility to continue to increase oxytocin dosage.

Patient recruitment, enrollment and entering randomization

Pregnant women at \geq 37 weeks presented to labor and delivery for induction of labor meeting the inclusion criteria with no exclusion criteria as stated above will be approached for recruitment and enrollment into this study. As stated previously, patients can be recruited and consented from the outpatient clinic as well. The study staff will provide informed consent to all patients. Risk and benefits of the study will be explained to each eligible patient.

After the consent is obtained, patient will enter the randomization process when they are ready to receive oxytocin for their induction of labor. The investigator will inform the research pharmacy if the patient should be in the lean or obese cohort. The research pharmacy will then assign the next allocation (already pre-determined by the sequence allocation as detailed above) and send the appropriate medication to the 8th floor L&D. The research pharmacy will track the study allocations. There are 4 comparison group:

- 1. Control group: Lean cohort: BMI ≤25, at <20 weeks gestation or BMI ≤28 at a term gestation of pregnancy, low dose oxytocin protocol
- 2. Intervention group: Lean cohort: BMI ≤25, at <20 weeks gestation or BMI ≤28 at a term gestation of pregnancy, high dose oxytocin protocol
- 3. Control group: Obese cohort: BMI ≥30, at <20 weeks gestation or BMI ≥35 at a term gestation of pregnancy, low dose oxytocin protocol

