4. Intervention group: Obese cohort: BMI ≥30, at <20 weeks gestation or BMI ≥35 at a term gestation of pregnancy, high dose oxytocin protocol

Lean cohorts will be randomized into the low dose or high dose oxytocin arm. The obese cohorts will also be randomized into the low dose or high dose oxytocin arm.

Protocol for each comparison group

Management of oxytocin induction in this study follows normal standard of care on labor and delivery nationally. The only part which will be done specifically for research is the higher concentration of oxytocin given in this study in the high dose oxytocin arm.

Per routine care, oxytocin dosage is titrated up or down to achieve labor while maintaining patient safety. Patient safety is continuously monitored with the tocometer (to monitor for maternal uterine contractions) and fetal heart tracing (to monitor for fetal well being). Stopping rules are listed under each arm separately.

1) Lean, low dose oxytocin arm

Oxytocin will be administered as described above via a slow intravenous infusion pump. Under the supervision of the study investigator, the patient's nurse will increase the oxytocin infusion as described above, start at 2cc/hr, increase 2cc/hr every 30 minutes up to 20cc/hr. The oxytocin will be increased until one of the parameters below were met:

>200 Montevideo unit on an intrauterine pressure catheter

3-5 uterine contractions in a 10-minute period on the external uterine tocometer cervical change and progression of labor

Tachysystole is defined as more than 5 contractions in 10 minutes over an average of a 30 minutes period. In the setting of tachysystole with reassuring fetal status, the oxytocin would be decreased by increments of 2cc until tachysystole no longer occurs. In the setting of nonreassuring fetal status (determined by the provider based on the fetal heart tracing), the oxytocin infusion would be turned off and restarted at ½ of the previous dose after 30 minutes, as long as fetal heart tracing recovers.

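### The consent message says agreeing brings no change in clinical care, but half of the women randomized receive three times the site's standard oxytocin concentration

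*Combined protocol and SAP*

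**What the plan says.** Section 7(b), Informed Consent, sets out what will be communicated to patients: "there will be no change in their clinical care, regardless if patient agreed to consent with this study". An example follows, that taking part does not alter the pain-management options routinely available. The stated purpose comes next: "This will minimize the potential for coercion". The section then adds: "Patients who decline enrollment in the trial will have the method of induction chosen by their physician".

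Section 8 describes what happens to women who agree and are randomized.

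- **Preparation and allocation** (Sequence generation for randomization, Allocation method and Blinding): "Single (low dose) and triple (high dose) concentration of oxytocin will be premixed in the intravenous fluid bag in the pharmacy". Allocation is 1:1 within the obese and lean cohorts, and investigators, providers, patients and analysts are blinded to the concentration.
- **Local standard** (Study Drug): "Low dose oxytocin regimen (the standard at Banner University Labor and Delivery, as well as across the United States".
- **Research element** (Protocol for each comparison group): the only part "done specifically for research is the higher concentration of oxytocin given in this study in the high dose oxytocin arm".

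Two other statements bear on the consent discussion. Section 7(a) says there is no script and that the sections of the consent form guide the conversation. Section 8, under Patient recruitment, enrollment and entering randomization, says that risks and benefits will be explained to each eligible patient.

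**The concern.** The assurance covers both choices. As worded, it tells a woman that her clinical care is the same whether she agrees or declines. The protocol's own procedures say otherwise for a woman who agrees and is randomized, and the difference lies in the single experimental element of the trial.

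At stake is the accuracy of what staff are told to say. With no script, an explicit statement of what will be communicated carries weight. Staff who follow it would give participants a statement that section 8 contradicts, even if the same conversation also covers randomization and dose. A woman could then hear two messages that do not agree.

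**Working it through.** **Inputs**

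- Low-dose bag: 30 units in 500 cc (section 8, Study Drug).
- High-dose bag: 90 units in 500 cc (same place).
- Pump rates, identical in both arms: start at 2 cc/hr, with provider assessment at 20 cc/hr (same place).
- Allocation: 1:1 within each BMI cohort (section 8, allocation paragraph).
- Group sizes: 35 in each of 4 groups, 140 in total (section 6).

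**Step 1. Reproduce the protocol's concentrations**

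Concentration = units × 1,000 / volume.

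- Low dose: 30 × 1,000 / 500 = 60 miliunit/cc.
- High dose: 90 × 1,000 / 500 = 180 miliunit/cc.
- Ratio: 180 / 60 = 3, which agrees with the protocol's single and triple description.

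**Step 2. Delivered dose at the same pump rate**

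Dose per minute = concentration × pump rate / 60.

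| Pump rate | Low dose (miliunit/min) | High dose (miliunit/min) |
|---|---|---|
| 2 cc/hr | 60 × 2 / 60 = 2 | 180 × 2 / 60 = 6 |
| 20 cc/hr | 60 × 20 / 60 = 20 | 180 × 20 / 60 = 60 |

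These match the figures in the Study Drug paragraph. At any given pump setting the delivered dose is tripled along with the concentration.

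**Step 3. How many women**

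High-dose share = (35 + 35) / (4 × 35) = 70 / 140 = 50%. Within each cohort it is 35 / 70 = 50%. The base is women randomized. Section 7 treats consented women who labor spontaneously or rupture membranes before presentation as screen failures, so the share of all women who consent is not fixed by the plan.

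**Step 4. The assurance against the procedures**

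| Group | What section 8 or 7(b) provides | Does the assurance hold? |
|---|---|---|
| Declines | Physician chooses the induction method | Yes |
| Randomized, low dose (70 planned) | Site-standard concentration, but set by the list and blinded to patient and providers | On concentration, yes; on who selects the regimen and who knows the concentration, no |
| Randomized, high dose (70 planned) | Three times the site-standard concentration, set by the list, blinded, and described as done for research | No |

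A treatment given only because a woman is in the study is a change in her care. Sections 7(b) and 8 cannot both stand as worded.

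**The case against.** The strongest reply is that the sentence is being read out of context. Its declared aim is to limit coercion, and the text goes on to say what happens to women who decline. The natural intention is that refusal carries no penalty and that other routine care is unaffected. That is probably what was meant. The literal conflict remains, however, because the wording expressly extends to women who agree and the pain-management example is about taking part.

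The second reply is that women may be properly informed all the same. The consent form is a listed attachment that guides the discussion, and section 8 promises an explanation of risks and benefits. This stands, and it limits the finding. A reader might infer that the tripled concentration is withheld, that consent is invalid for every randomized woman, or that withdrawals will follow once the difference becomes known. The documents support none of these. The form cannot be examined, the assurance may simply sit beside a full disclosure, and section 6 anticipates few withdrawals.

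Third, the high-dose regimen is described as professionally endorsed and widely used internationally, blinding of providers is ordinary in a double-blind trial, and staff are briefed on the study. Providers also keep their discretion over fetal status, mode of delivery and any increase beyond 20 cc/hr. All of this is correct, and it means the low-dose women's care differs little from usual. It bears on risk and on the extent of the change. It does not make the assurance accurate, because a regimen that is not the site's standard is still a change from the care given there.

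**Conclusion.** The point holds as an internal contradiction. The assurance in section 7(b) is accurate for women who decline. It is inaccurate on concentration for the 70 of 140 planned participants assigned to high dose (180 against 60 miliunit/cc). For all 140 it is inaccurate in two narrower respects: the regimen is chosen by list, and the concentration is not known to the woman or her providers.

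This rests on the planned group sizes being met and on a plain reading of the sentence. It does not rest on the content of the consent form, and it says nothing about the acceptability of either regimen. No estimand, sample size or analysis is affected. The sentence should be corrected because it concerns the trial's only experimental element and the correction is simple.

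**What to change.** Replace the assurance in section 7(b) with wording along these lines:

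> Declining will not change your care. If you agree, you will be assigned by chance (1 in 2) to the usual oxytocin concentration or to three times that concentration, and neither you nor your providers will know which. Other routine care, including your options for pain relief, is not affected.

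This keeps the protection against coercion and uses only facts already in sections 7 and 8. Reconcile the new wording with the paragraph in section 8 that names the higher concentration as the research element. Check the consent form for the same assurance and amend it if it appears there.

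The cost is a wording change to the consent process, and to the form if needed. A few women may decline who would otherwise have agreed. No dose, procedure or analysis changes.
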